#### **8.3.2.2.3 SDS**

Mean change from baseline compared with placebo in mean SDS total score using MMRM.

The mean SDS total score and each domain (absolute, change from baseline) will be summarized by visit. The number of days lost and days underproductive will also be summarized by visit.

#### **8.3.2.2.4 PCL-5**

Mean change from baseline compared with placebo in PCL-5 score using MMRM.

Besides, the PCL-5 score (absolute, change from baseline) will also be summarized by visit.

#### **8.3.2.2.5 CGI-S**

Mean change from baseline compared with placebo in CGI-S using MMRM.

Besides, the CGI-S (absolute, change from baseline) will also be summarized by visit.

The CGI-S will also be summarized by N (%) of the categorical values (i.e., 1, 2, 3, 4, 5, 6, 7).

#### **8.3.2.2.6 PGI-S**

Mean change from baseline compared with placebo in PGI-S using MMRM.

Besides, the PGI-S (absolute, change from baseline) will also be summarized by visit.

The PGI-S will also be summarized by N (%) of the categorical values (i.e., 1, 2, 3, 4, 5).

#### **8.3.2.2.7 BDI-II**

Mean change from baseline compared with placebo in BDI-II score using MMRM.

Besides, the BDI-II score (absolute, change from baseline) will also be summarized by visit.

#### **8.3.2.2.8 WEMWBS**

Mean change from baseline compared with placebo in WEMWBS score using MMRM.

Besides, the WEMWBS score (absolute, change from baseline) will also be summarized by visit.

#### **8.3.2.2.9 PSQI**

Mean change from baseline compared with placebo in PSQI score using MMRM.

Besides, the PSQI score (absolute, change from baseline) will also be summarized by visit.

#### **8.3.2.2.10 PGI-C**

The number and percentage of each level the PGI-C will be summarized.

Improved items include: “Very much improved”, “Much improved”, “Slightly improved”.

The number and percentage of improved rate on the PGI-C will be summarized and compared between treatment groups using CMH test.

#### **8.3.2.2.11 CGI-I**

Improved items include: “Very much improved”, “Much improved”, “Minimally improved”.

The number and percentage of improved rate on the CGI-I will be summarized and compared between treatment groups using CMH test.

## 8.4 Safety Analysis

All safety analyses will be performed on the Safety Population. No formal statistical analyses of safety analysis were planned.

Safety assessments will include clinical laboratory evaluations (clinical chemistry, hematology and urinalysis), vital signs (HR, BP and body temperature), 12-lead ECG, physical examinations, C-SSRS and AE monitoring.

To assess the safety and tolerability of oral methylone compared to placebo administered weekly over 4 weeks in participants with PTSD:

- Incidence and severity of TEAEs
- Incidence and severity of AESIs
- Change in HR, SBP, DBP and temperature during each dosing session
- Clinically significant changes in ECG
- Changes from baseline in clinical laboratory parameters (clinical chemistry, hematology, and urinalysis)

### 8.4.1 Adverse Events

Treatment-emergent AEs (TEAE) are defined as any AE with an onset date on or after the date of first administration of study treatment and not more than 7 days after the last dose unless otherwise suspected to be related to study drug. For AEs with missing or partial start dates, if there is no clear evidence that the AEs started before or after study treatment, the AEs will be classified as TEAEs. Suspected to be drug related TEAEs include Relationship to study drug: “Possibly Related”, “Probably Related”.

An overall summary of the number and percentage of subjects with below will be presented:

- Any TEAEs
- serious TEAEs
- TEAEs related to study drug
- serious TEAEs related to study drug
- TEAEs leading to study discontinuation
- TEAEs leading to drug withdrawn
- TEAEs leading to death
- TEAEs of special interest.

Also, the TEAEs will be presented by System Organ Class (SOC), and PT. Subjects will be counted only once for each SOC and PT.

In addition, subjects with TEAEs in various severity categories will be presented based on the maximum severity of a specific TEAE for a subject. Similarly, subjects with TEAEs in various relationship categories will be presented based on the most related relationship (from ‘not related’, ‘unlikely related’, ‘possibly related’, to ‘probably related’) of a specific TEAE for a subject.

All AEs will be presented in individual by-subject data listings. Listings of any subject experiencing TEAEs related to study drug, AESI and an SAE will be provided separately.

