## 7.8.1 Reporting Procedures and Requirements

### 7.8.1.1 Time Period and Frequency for Collecting AE and SAE Information

All SAEs will be collected from the signing of the informed consent form (ICF) until the EOS visit at the timepoints specified in the Schedule of Assessments (see [Section 1.3](#)).

All AEs will be collected from enrollment/randomization until the EOS visit at all interactions with the participants (see [Section 1.3](#)). A baseline safety assessment will occur after Screening. Medical occurrences that begin before the start of study intervention but after obtaining informed consent will be recorded as medical history/current medical conditions, not as AEs.

The Investigator is not obligated to actively seek information on AEs or SAEs after conclusion of the study participation. However, if the Investigator learns of any SAE, including a death, at any time after a participant has been discharged from the study, and the Investigator considers the event to be reasonably related to the study intervention or study participation, the Investigator must promptly notify the Sponsor.

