### 7.8.1.3 *Serious Adverse Events*

Each AE will be assessed to determine whether it meets seriousness criteria ([Section 7.7.1.2](#)). If the AE is considered serious the Investigator must report this event to the Sponsor or delegate. The Sponsor or delegate will report the event to the IRB/EC according to relevant standard operating procedures (SOPs). Serious adverse events occurring from the time of signed informed consent to the EOS visit or 7 days after the last administration of study drug (whichever occurs later) will be recorded in source and electronic data capture. All serious, treatment-related adverse events, regardless of the time of onset after treatment, should be reported. All information about SAEs will be collected and reported via the SAE form and sent by email message (contact information will be contained in the Investigator site file). At a minimum, the initial report should include the following information:

- Event
- Seriousness criteria
- Protocol number
- Participant number and year of birth
- Study drug (blinded for Part B unless unblinding is required for medical management)
- Reporter name and contact information

In the case of a “minimum report” (one that solely comprises the information bulleted above), a more detailed Follow-Up report should be sent as soon as more information becomes available but no later than 7 calendar days after the date of the initial report. Each SAE should be followed up until resolution or stabilization and for reported deaths, the Investigator should supply Sponsor, or designee, and the IRB/EC with any additional requested information (e.g., autopsy reports and terminal medical reports), if available. The original SAE form should be kept at the study site. The Investigators will be responsible for determining and in turn, reporting SAEs to the Sponsor. The Sponsor, or designee, will be responsible for reporting SAEs to regulatory authorities according to the applicable regulatory requirements. The Sponsor, or designee, will be responsible for completing the safety reports and for notifying the relevant authorities of any SAE as outlined in the International Council for Harmonisation (ICH) Guidelines and per local regulatory requirements.

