##### *9.5.1.1 Adverse Events*

All AEs will be listed according to system-organ class (SOC) and preferred term (PT) assigned to the event using Medical Dictionary for Regulatory Activities (MedDRA). The number and percentage of participants experiencing any AEs will be summarized overall and by treatment for Part B, causality and maximum severity. Any SAEs, TEAEs and/or AEs that led to withdrawal will also be listed in the same manner.

The number and percentage of participants experiencing TEAEs, SAEs, and AEs leading to withdrawal from the trial drug will be tabulated by MedDRA SOC, PT, causality, and maximum severity. The AE tables will also include frequency counts for each SOC and PT.

All AESIs will be summarized similarly to the AEs.

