## 11.2 Appendix 2 Mock Shell of Tables, Figures and Listings

The information and explanatory notes to be provided in the footnote or bottom of each table, figure and listing will include the following information: date and time of output generation; SAS program name; any other output specific details (for example, definition of abbreviations) that require further elaboration.

Some of the TFLs may not have sufficient numbers of subjects or data for presentation. If this occurs, the blank TFL shell will be presented with a message printed in the table, such as, “No data available for this report”.

The treatment and subject number will be included in all data listings. All listings will be sorted by treatment group, subject number, parameter and date, as applicable.

See separate file for mock shell of tables, figures and listings.

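### The adverse event tables named in the SAP count only TEAEs, so SAEs, deaths and AESIs that start more than 7 days after the last dose and are rated unrelated get no by-arm count, although the protocol plans one

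*SAP*

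**What the plan says.** **Collection.** Protocol 7.8.1.1: "All AEs will be collected from enrollment/randomization until the EOS visit at all interactions with the participants". For SAEs, Protocol 7.8.1.3 says that events from consent "to the EOS visit or 7 days after the last administration of study drug (whichever occurs later) will be recorded". The end-of-study visit is nominally Day 64, six weeks after the fourth dose on Day 22.

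**Planned tabulation in the protocol.** Section 9.5.1.1 contains three statements that bear on this point:
- "The number and percentage of participants experiencing any AEs will be summarized overall and by treatment for Part B, causality and maximum severity".
- Counts with percentages for those "experiencing TEAEs, SAEs, and AEs leading to withdrawal from the trial drug will be tabulated by MedDRA SOC, PT". The same tables are also split by causality and by worst severity.
- "All AESIs will be summarized similarly to the AEs".

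None of the three limits any AEs, SAEs or AESIs to a window after the last dose.

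**Tabulation in the SAP.** Section 8.4.1 defines a TEAE as an event starting on or after the first dose "and not more than 7 days after the last dose unless otherwise suspected to be related to study drug". Related means possibly or probably related. The overall summary has eight rows, all of them TEAE rows: any, serious, related, serious related, leading to study discontinuation, leading to drug withdrawal, fatal, and special interest. The tables by system organ class and preferred term, by maximum severity and by relationship also count TEAEs only.

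**Listings in the SAP.** All AEs are listed by subject. In addition, "Listings of any subject experiencing TEAEs related to study drug, AESI and an SAE will be provided separately". SAP Appendix 2 adds: "All listings will be sorted by treatment group, subject number, parameter and date, as applicable".

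**Declared changes.** SAP section 1 says its methods are the protocol's unless otherwise stated with reasoning. SAP 9.1 lists seven changes, and none concerns adverse event tables.

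**The concern.** The incidence and severity of AESIs is a Part B secondary endpoint in the protocol and is repeated without a TEAE limit in SAP 8.4. The only AESI summary that SAP 8.4.1 names is the TEAE row, so the endpoint would be counted for only part of follow-up. The same holds for SAEs and deaths: the serious row could show zero in an arm while the listing holds an event.

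The rule also makes inclusion of a late event depend on the investigator's causality rating. In a placebo-controlled comparison, counts regardless of causality let the placebo arm show the background rate. A table that admits late events only when they are judged related gives up that comparison for the follow-up period.

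The gap is clearest for abuse-potential AESIs. The Schedule of Assessments shows no drug-use assessment after Day 22, so AE reporting is the scheduled route for a late signal, and the unredacted SAP has no other by-arm summary of such events. Late suicidality is less exposed, because SAP 8.4.6 summarizes the C-SSRS for all time after first dose. There, only the suicide-risk AESI count is cut short.

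**Working it through.** The documents give no figure for this point to reproduce. The check is a comparison of text plus calendar arithmetic.

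**Step 1. Compare the tables.**

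| Category | Protocol 9.5.1.1 | SAP 8.4.1 |
|---|---|---|
| Any AE | Number and percentage, by treatment in Part B | TEAE only |
| SAE | Tabulated as its own category beside TEAEs | Serious TEAE only; all SAEs listed |
| Death | Not named; falls under SAEs | Fatal TEAE only; otherwise listed |
| AESI | All summarized in the same way as AEs | TEAE of special interest only; all AESIs listed |

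The seven changes in SAP 9.1 are: extra CAPS-5 and MADRS derivations, missing-data rules, a physical-examination shift table, SDS scoring, mITT in place of ITT, one-sided testing, and sex as a covariate. None covers the table above.

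**Step 2. Length of the uncounted period.** Inputs from the Schedule of Assessments: last dose Day 22 (±1), end of study Day 64 (±3). Input from SAP 8.4.1: a 7-day window.

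- Window end = last dose day + 7. Days outside = end-of-study day − window end.
- Nominal: 22 + 7 = 29; 64 − 29 = 35 days (Days 30 to 64); 35/64 = 54.7%.
- Shortest, with last dose Day 23 and end of study Day 61: 61 − 30 = 31 days; 31/61 = 50.8%.
- Longest, with last dose Day 21 and end of study Day 67: 67 − 28 = 39 days; 39/67 = 58.2%.
- Dosing stopped early, assuming follow-up still runs to Day 64: last dose on Day 1, 8 or 15 leaves 64 − 8 = 56, 64 − 15 = 49 or 64 − 22 = 42 days outside.

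**Step 3. Scheduled AE contacts.** The AE row runs from Visit 3 to Visit 19, which is 17 contacts. Visits 16 to 19 (Days 36, 43, 57 and 64) come after nominal Day 29: 4/17 = 23.5%.

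**Step 4. An event of the affected type.** Protocol 2.4.1 reports one SAE among the 14 Part A participants, unrelated and 20 days off drug. That is 1/14 = 7.1% with an SAE. Since 20 > 7 and the event was rated unrelated, the SAP 8.4.1 rule would give 0/14 in the serious row. The SAP governs Part B only, so this illustrates the rule and does not restate Part A.

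**The case against.** **The window is the SAP's to define.** The supplied protocol text gives no TEAE window, and Protocol 9.3 leaves algorithms to the SAP and allows methods to change. A 7-day window suits acute tolerability of a drug that the protocol describes as having a short half-life. This stands. The fault lies in putting TEAE-only tables where the protocol named any-AE, SAE and AESI tables, without saying so.

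**The loss is narrow and nothing is hidden.** Late events rated possibly or probably related stay in the tables, and the protocol's definition of possibly related is broad. All AEs are listed by treatment group, and with about 64 participants the late serious events may be few enough to read off a listing. A death would also enter the disposition table as a discontinuation reason. In Part A, the protocol disclosed the late SAE separately. All of this limits the harm. But a listing or a disposition reason is not the count and percentage by arm that Protocol 9.5.1.1 plans.

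**The missing tables may still be planned.** The shells are in a separate file that was not available, and SAP section 1 adopts protocol methods by default. An all-SAE or all-AESI shell cannot be excluded. The default, however, speaks of the methods that the SAP discusses, and 8.4.1 discusses these summaries in TEAE form. If wider tables exist in the shells, the SAP text should name them.

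**The size is calendar time, and safety is descriptive.** Both are true. No event count can be derived from 55% of days, and no test, estimate or power figure changes. A separate display of the post-window period also goes beyond what the protocol requires.

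**Conclusion.** The concern holds. Followed as written, SAP 8.4.1 gives by-arm counts of SAEs, deaths and AESIs that leave out events starting more than 7 days after the last dose and rated not or unlikely related. Protocol 9.5.1.1 would count them, and SAP 9.1 does not declare the difference.

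For a four-dose completer the uncounted period is 35 of 64 days (55%; 51% to 58% across visit windows), covering 4 of 17 scheduled AE contacts. The number of events affected cannot be estimated from the documents; Part A shows only that one such event occurred among 14 participants.

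The conclusion rests on the tables that the SAP text names, on the unredacted text, and on reading the protocol's any-AE, SAE and AESI summaries as unrestricted, since no limit is stated there. It should be corrected before the SAP is applied. The listings keep the individual data available.

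**What to change.** 1. Keep the 7-day TEAE tables as the acute-tolerability display.
2. Add by-arm descriptive tables, regardless of causality, of all AEs, SAEs, deaths and AESIs from first dose to the end-of-study visit. Use the SOC, PT, causality and maximum-severity breakdowns of Protocol 9.5.1.1.
3. State in SAP 8.4 that the AESI secondary endpoint is taken from the full-period table.
4. Preferably show the period after the 7-day window as its own column or table, so that late events are not mixed with acute ones. This is a useful extra, not a protocol requirement.
5. In SAP 9.1, record that the SAP sets the 7-day TEAE window, and declare with a reason any table that stays TEAE-only in place of one named in Protocol 9.5.1.1.
6. Bring the table shells into line with the revised text.

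The cost is a few extra descriptive tables from data already collected, with no added visits or testing. The drawback is that late background events will be shown too; the placebo column lets the reader judge them.

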### 8.4.2 Laboratory Tests

Clinical laboratory data will be summarized using descriptive statistics for the measured values and change from baseline for each parameter. The shift table (high, normal, low) is used to describe the clinical evaluation changes of laboratory tests prior and post the first dose.

Data listings will include the results of clinical laboratory evaluation, drug screen use, and pregnancy test.

### 8.4.3 Vital Signs

**Per dosing session:** Baseline is defined as the measurements of pre-initial dose during each dosing session.

**Per participant:** Baseline is defined as the measurements collected at Visit 2. Post-baseline vitals were collected at Visit 15.

Where multiple values are recorded at a time for a participant, the mean of the values will be used in the descriptive statistics.

Descriptive statistics for the measured values and change from baseline will be calculated and plotted for each parameter by treatment and timepoint.

Vital signs (SBP, DBP, HR, respiratory rate and body temperature) will be listed for individual participants.

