#### **6.2.1.3 Adverse Events of Special Interest**

The Sponsor will pay special attention to a subset of AEs; these AEs will be marked in the eCRF with the denotation AESIs whether serious or non-serious. Adverse events of special interest (AESI) include:

- Grade 3 hypertension, SBP  $\geq 160$  mmHg or DBP  $\geq 100$  mmHg, requiring the need for medical intervention with more than one drug or more intensive therapy than previously used.
- Significant cardiovascular events
- AEs related to suicide risk, such as; suicides, suicide attempts, self-injurious behavior associated with suicidal ideation and suicidal ideation judged to be serious or severe in the opinion of the Investigator.
- Signals of abuse potential AE involving terms of behavioral addiction, drug abuser, substance abuser.

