### **8.1.1 General Rules**

Continuous variables will be summarized using the following descriptive summary statistics: the number of subjects (n), arithmetic mean, standard deviation (SD), standard error (SE), median, minimum value (Min), and maximum value (Max). The decimal places of Mean and Median will be formatted to one more than the original value. The decimal places of SD and SE will be formatted for two more than the original value. The decimal places of Min and Max will be formatted with the same as original value. The number of decimal places cannot exceed 4.

Frequencies (n) and percentage (%) will be used to summarize categorical data, and percentage is formatted for one decimal place. If the percentage is 0, then percentage is set to null. If the percentage is 100, then it is formatted as 100.0.

The derived data will reserve one more decimal place than the original. Descriptive statistics of derived data follow the above rules.

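### SAP 8.4.3 names no per-participant peak and no count of participants reaching a stated blood pressure or temperature level during dose sessions

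*SAP*

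**What the plan says.** SAP 8.4 lists "Change in HR, SBP, DBP and temperature during each dosing session" among the safety assessments, and Protocol Table 2 has it as a Part B safety endpoint. SAP 8.4.3 sets baseline for each session as the reading before the initial dose and then plans: "Descriptive statistics for the measured values and change from baseline will be calculated and plotted for each parameter by treatment and timepoint". SAP 8.1.1 defines these statistics as n, mean, SD, SE, median, minimum and maximum. SAP 8.4.3 adds that vital signs "will be listed for individual participants".

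Two rules govern extra readings. For several values at one time, SAP 8.4.3 says: "Where multiple values are recorded at a time for a participant, the mean of the values will be used in the descriptive statistics". Data from unscheduled visits or assessments are listed but not summarised (SAP 8.1.4).

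On the adverse event side, SAP 8.4.1 includes one overall line for "TEAEs of special interest", and Protocol 9.5.1.1 says "All AESIs will be summarized similarly to the AEs". SAP 6.2.1.3 makes hypertension at SBP of at least 160 or DBP of at least 100 mmHg an AESI only when "requiring the need for medical intervention with more than one drug or more intensive therapy than previously used". Temperature is not on the AESI list.

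By contrast, the SAP plans shift tables for laboratory tests (8.4.2), ECG (8.4.4) and physical examination (8.4.5).

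**The concern.** Blood pressure and heart rate rises are the acute effect the protocol expects (Protocol 5.6.5), and Protocol 4.5 calls them the most common safety findings. The protocol also reasons in numbers of participants: under Protocol 4.9, two participants meeting the stated hypertension or temperature criteria interrupt enrolment. The final analysis has no matching count taken from the measured values.

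A table of statistics by timepoint shows the average course and the single most extreme value at each time. It does not say how many people had a high reading at any time in a session, or in any of the four sessions. Individual peaks fall at different times, so the highest point of the mean curve is also lower than the mean of individual peaks. What is at stake is what the trial can report about individual pressor and temperature responses, in a study meant to inform the design of later trials (SAP 8.1.5).

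**Working it through.** **Step 1: which planned summaries could give the count?**

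- *By-timepoint statistics (SAP 8.4.3, 8.1.1).* Maximum shows that at least one participant reached a level at that time. It does not show how many did, or whether the maxima at different times belong to the same person.
- *AESI line (SAP 8.4.1, 6.2.1.3).* Counts Grade 3 hypertension with escalated therapy, pooled with three other AESI types. A reading of 160/100 without escalation is outside it, and so is temperature.
- *Other adverse event tables (SAP 8.4.1).* Count an elevation only if the investigator reports it as an adverse event.
- *Disposition (SAP 8.2.1).* A participant stopped under the temperature rule would be among the discontinuations, but nothing says the reason would identify temperature.
- *Listings (SAP 8.4.3).* Hold the readings, with no count.

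**Step 2: how many readings are involved?** Blood pressure is taken every 30 minutes over sessions of about 8 hours (Protocol 1.3, 4.2): 8 × 2 = 16 post-dose readings per session, and 16 × 4 = 64 per participant. Temperature is hourly: 8 per session, 32 in all.

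**Step 3: how far can the mean and the count diverge?** The documents give no figure to reproduce, so this is an illustration.

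- From the documents: mean peak SBP rise 25.2 mmHg at 200 mg in healthy volunteers (Protocol 2.4.2); 32 participants per arm (Protocol 9.2).
- Assumed: predose SBP mean 115 to 125 mmHg; SD of the peak-time reading 10 to 15 mmHg; normal distribution.
- Formula: share = P(Z ≥ (160 − m)/SD), with m = predose mean + 25.2.

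| Predose mean | SD | Arm mean at peak | (160 − m)/SD | Share ≥160 | Of 32 |
|---|---|---|---|---|---|
| 115 | 10 | 140.2 | 1.98 | 2.4% | 0.8 |
| 115 | 15 | 140.2 | 1.32 | 9.3% | 3.0 |
| 120 | 12 | 145.2 | 1.23 | 10.9% | 3.5 |
| 125 | 10 | 150.2 | 0.98 | 16.4% | 5.2 |
| 125 | 15 | 150.2 | 0.65 | 25.7% | 8.2 |

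**Step 4: can the number of distinct participants be recovered from the mean and SD?** At one timepoint, roughly, under normality. Over four sessions, no. In the middle row, 10.9% per session allows anything from 10.9% (the same people each time, 3.5 of 32) to 4 × 10.9% = 43.6% (different people each time, 14 of 32). Simulation with one peak reading per session gave 23% (7.4 of 32) at within-person correlation 0.7 and 32% (10.2 of 32) at 0.3. The planned statistics at each timepoint would be the same in expectation in both cases. Over the whole assumed range, with correlation 0.3 to 0.7, the share reaching 160 mmHg at least once ran from about 6% to 60% (2 to 19 of 32).

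**Step 5: what does averaging do?** It applies only to values recorded at the same time. Readings of 164 and 154 average to (164 + 154)/2 = 159, so a crossing can disappear that way.

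**The case against.** The case against making much of this is substantial, and most of it stands.

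- A reader might infer that only arm means are reported. That is wrong: SD, median, minimum and maximum are planned, with plots and listings, so a wide spread or an extreme value would be visible.
- A reader might infer that averaging dilutes the session profile, or removes the very readings that prompted a repeat. The scheduled 30-minute readings stay separate, and no text says a high value triggers a same-time repeat. Protocol 5.6.5 ties extra measurements to symptoms.
- A reader might infer that an untreated high reading can appear in no count. Protocol 7.7.1.1 lets a clinically significant abnormal finding be reported as an adverse event, and SAP 8.4.1 would then count it.
- The protocol's levels carry conditions. Its 160/100 rule requires escalated intervention. In Protocol 4.9, 140/90 matters only if it persists over 48 hours and needs intervention. The dosing-stop rule for temperature needs a rise above 2°C and also a reading of at least 38°C. There is no on-dose heart rate threshold. Bare readings should not be called breaches of protocol rules.
- The 25.2 mmHg rise comes from a different dose and population. Protocol 2.4.2 describes the effect as dose-dependent, and Protocol 4.5 expects the split regimen to lower the peak concentration relative to a single 250 mg dose.
- Table shells are in a separate file (SAP 11.2), the DSMB reviews vital signs during the trial (Protocol 4.7), and a count could be made from the listings.

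What remains is narrower. The SAP text does not specify the count, the nearest line excludes unescalated readings and temperature, and a count made later from listings would use cut-offs chosen after the data were seen.

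**Conclusion.** The gap is real but limited to reporting. As far as the SAP text goes, the number of distinct participants reaching a given blood pressure or temperature during dose sessions cannot be obtained from any named summary. It is clearest for SBP of at least 160 or DBP of at least 100 mmHg without escalated therapy, and for temperature. The contents of the separate shells are unknown.

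The illustrative size is about 2% to 26% at the peak timepoint, on the assumptions in step 3. A smaller rise in this trial would lower those shares, and at the low end the figure is about one participant. It would therefore be wrong to conclude that a sizeable minority will exceed 160 mmHg. The width of the range is the reason to tabulate the count. The primary efficacy analysis is not affected. The change is worth making because it is cheap and concerns a named safety endpoint.

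**What to change.** In SAP 8.4.3:

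1. For each participant and session, derive the highest individual (unaveraged) post-dose SBP, DBP, heart rate and temperature, and the largest rise from that session's predose value. Include readings during the session that are classed as unscheduled, as a stated exception to SAP 8.1.4.
2. Summarise these peaks and rises by arm.
3. Tabulate number and percentage by arm, per session and over all sessions, with SBP of at least 160 or DBP of at least 100 mmHg regardless of intervention; with a temperature rise above 1°C; with a rise above 1.5°C; and with a rise above 2°C together with a reading of at least 38°C.
4. For heart rate give only the peak and rise summary.

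State that these are reporting cut-offs and change no clinical rule. In SAP 8.4.1, report the AESI line by type.

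The cost is one derivation and one table from data already collected. Maxima of single readings are noisier than averages and some will be high by chance, so the placebo arm must be shown alongside.
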